8.1.11 Central Laboratory Standard Evaluations

[Table 7](#) lists the standard parameters to be analyzed by the Central Laboratory. Please refer to [Table 8](#) for the Liver Biochemistry Panel sampling frequency and the Schedule of Events for the related time points.

Protocol VTX-801_CLN_001	Investigational Product: VTX-801
	Version: 9 dated 07 AUG 2023
	Author: Aixial Group CRO

Table 8 Standard Parameters to be Analyzed by the Central Laboratory

Hematology	Blood Biochemistry	Urinalysis	Others
CBC: 
 • Hematocrit • Hemoglobin • Relative reticulocyte counts • Red blood cell (RBC) Count • Differential and absolute WBC count • Platelet count • Mean cell volume Coagulation: 
 • INR • Activated Partial Thromboplastin time (aPTT) • Fibrinogen assay 	
 • Glucose • Total protein • Albumin • Creatinine • Creatine kinase • Total cholesterol • Triglycerides • Sodium • Potassium • Chloride • BUN • CRP 
Liver biochemistry panel:
 
 • ALT • AST • GGT • LDH • Total bilirubin • Direct bilirubin • ALP 
Lipid Panel (fasting):
 
 • Low-density lipoprotein (LDL) • High-density lipoprotein (HDL) • Total cholesterol • Triglycerides 	
 • Urobilinogen • Nitrites • Glucose • Protein • Ketones • Leukocyte esterase • Bilirubin • Specific gravity • Color • Appearance • Occult blood • pH 	
 • Antibodies anti-HIV-1, anti-HIV-2, anti-HTLV-1 and anti-HTLV-2 • HBS antigen and antibodies anti-HBC • Antibodies anti-HCV 
(Note: not to be performed if previous viral RNA assays in two samples, collected at least 6 months apart, are negative (cf. exclusion criterion)).
 
 • ATP7B genotyping • Alpha-fetoprotein • Serum pregnancy test

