Abbreviations: ATP7B= Copper-transporting P-type ATPase; ALP= ALkaline Phosphatase; ALT= ALanine aminoTransferase; aPTT= activated Partial Thromboplastin Time; AST= ASpartate aminoTransferase; BUN= Blood Urea Nitrogen; CBC= Complete Blood Count, GGT= Gamma-Glutamyl Transpeptidase; HBC= Hepatitis B Core antibody; HBS antigen= Hepatitis B Surface antigen; HCV= Hepatitis C Virus; HIV= Human Immunodeficiency Virus; HTLV= Human T-cell Lymphotropic Virus; INR= International Normalized Ratio; LDH= Lactate DeHydrogenase; LDL= Low-Density Lipoprotein; RBC= Red Blood Cell; RNA= RiboNucleic Acid; WBC White Blood Cell

In relation to the Sirolimus treatment, patients will be monitored for hyperlipidemia. A lipid panel consisting of low-density lipoprotein (LDL), high-density lipoprotein (HDL),

Protocol VTX-801_CLN_001	Investigational Product: VTX-801
	Version: 9 dated 07 AUG 2023
	Author: Aixial Group CRO

triglycerides and total cholesterol is included at Screening 1, Screening 2, Week 4 and Week 8.

Each patient will have a comprehensive surveillance plan which monitors liver enzymes and liver function tests post administration of VTX-801. It will include a test at each visit occurring either on site or at home (home nurse) and twice a week sampling between Week 4 and Week 12. Additionally, availability of laboratory results will be optimized in order to ensure quick Investigator accessibility to the results (less than 3 days) to make a decision on further action.

Furthermore, reports of abnormal ALT (defined as $\geq 1.5 \times$ baseline) will also be made available to Sponsor within 24 hours of the laboratory value being available (cf. Section 7.5.2).

Remnant blood and urine samples may be used for future biomarker explorations (excluding any genotyping) as data emerges; this will be the subject of an optional approval by patients in the informed consent (tick box).

Table 8 outlines the frequency of sampling of liver biochemistry parameters after VTX-801 administration, including both locally and centrally analyzed samples.

Protocol VTX-801_CLN_001	Investigational Product: VTX-801
	Version: 9 dated 07 AUG 2023
	Author: Aixial Group CRO

Table 9 Sampling Frequency of Liver Biochemistry Panel Following VTX-801 Administration

Period	Frequency
Weeks 1 to 3	Once a week
Weeks 4 to 12	Twice a week
Weeks 13 to 16	About Weekly, except for week 14
From Week 20 till End of Year 1	About monthly
Year 2	Every 3 months
Years 3-5	Every 6 months

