10.2 Visits 2-5: Baseline and Pre-VTX-801 Period

Duration: 4 study visits within a period of 7 days:

- **Visit 2;** Baseline: 1-day outpatient visit, which will also include the initiation of Sirolimus treatment [REDACTED].
- Flexibility of up to 7 additional days for VTX-801 administration is allowed if needed in order to comply with radiocopper production constraints or to accommodate the sites and/or patients. As a consequence, initiation of the

Protocol VTX-801_CLN_001	Investigational Product: VTX-801
	Version: 9 dated 07 AUG 2023
	Author: Aixial Group CRO

Sirolimus treatment [REDACTED] will then need to be shifted accordingly (start 7 days prior to VTX-801 administration).

- No visits for 3 days.
- **Visits 3-4-5:** a 3-day in- or outpatient visit period during [REDACTED].

Refer to [Table 2](#) Summary of Schedule of Events: Baseline to Week 12

(Note permitted visit windows are allowed for some assessments; refer to [Table 2](#) and its footnotes)

Visit 2	Day -7	Baseline	Outpatient visit	Cross-reference
Vital signs				Section 8.1.4
Physical examination				Section 8.1.3
Alcohol consumption				Section 7.7
Serum pregnancy test (for WOCBP only)				Section 8.1.12
Central Laboratory: blood/urine biochemistry; hematology; coagulation				Section 8.1.11
Central Laboratory: Liver biochemistry panel				Section 8.1.11
Local Laboratory: Liver biochemistry panel				Section 8.1.12
Calculation of MELD, APRI, FIB4 by CRO				Table 11
Ceruloplasmin (enzymatic assay and nephelometry), CuEXC, total Cu, REC, RAC, ANCC, CRP				Section 8.1.13
ELISA and IFN-gamma ELISpot				Section 8.2.4
Ophthalmology: slit lamp examination. It can be performed from Baseline V2 to the day before radiocopper administration as long as results are available before the day of radiocopper administration.				Section 8.1.6

Protocol VTX-801_CLN_001	Investigational Product: VTX-801 Version: 9 dated 07 AUG 2023 Author: Aixial Group CRO
--------------------------	--

For Visits 3-4-5, patients **from expansion cohort (only)** will be hospitalized, stay at a unit with clinical support or other location approved by the [REDACTED]

Refer to Table 2 Summary of Schedule of Events: Baseline to Week 12				
Visit 3	Day -3	Pre VTX-801	In or Out-patient visit	Cross-reference
Vital signs				Section 8.1.4

Protocol VTX-801_CLN_001	Investigational Product: VTX-801
	Version: 9 dated 07 AUG 2023
	Author: Aixial Group CRO

Physical examination	Section 8.1.3
Sirolimus	Section 7.5

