10.5.3 Visit 10 (Week 4 ± 2 days)

Importantly, from Week 4 to Week 12 inclusive post VTX-801 administration, liver function tests will be performed twice a week.

Additionally, in the case that an ALT increase $\geq 1.5 \times$ baseline between Week 4 and Month 6 post-VTX-801 administration occurs despite the immunosuppressive regimen (Section 7.5), site has to specifically refer to Section 7.5.2 for guidance.

Protocol VTX-801_CLN_001	Investigational Product: VTX-801
	Version: 9 dated 07 AUG 2023
	Author: Aixial Group CRO

Refer to Table 2 Summary of Schedule of Events: Baseline to Week 12				
Visit 10	Week 4 ± 2 days	Follow-up	Outpatient visit	Cross-reference
Vital signs				Section 8.1.4
Physical examination				Section 8.1.3
Alcohol consumption				Section 7.7
Central Laboratory: Blood/urine biochemistry with lipid panel; hematology; coagulation Fasting conditions are required for the lipid panel.				Section 8.1.11
Central Laboratory: Liver biochemistry panel				Section 8.1.11
Local laboratory: Liver biochemistry panel				Section 8.1.12
Ceruloplasmin (enzymatic assay and nephelometry), total Cu, REC, RAC, CuEXC, ANCC, CRP				Section 8.1.13
Anti-AAV3B capsid neutralizing antibodies				Section 8.2.1
Vector shedding: blood, urine, saliva, feces - mandatory Note: at all visits until end of year 1, as applicable, vector shedding sampling is to occur at every site scheduled visit until 3 consecutive concerned samples are negative (at or below quantification limit)				Section 8.2.3
ELISA and IFN-gamma ELISpot				Section 8.2.4
Sirolimus				Section 7.5
Sirolimus level test: sampling for blood trough concentration 28 days after starting treatment with Sirolimus				Section 7.5
Oral steroid (Prednisone or Prednisolone)				Section 7.5.1

Protocol VTX-801_CLN_001	Investigational Product: VTX-801
	Version: 9 dated 07 AUG 2023
	Author: Aixial Group CRO

Adverse events	Section 9.2
Concomitant medications	Section 8.1.2

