10.5.5 Visit 18 (Week 8 ± 2 days)

Refer to Table 2 Summary of Schedule of Events: Baseline to Week 12				
Visit 18	Week 8 ± 2 days	Follow-up	Outpatient visit	Cross-reference
Vital signs				Section 8.1.4

Protocol VTX-801_CLN_001	Investigational Product: VTX-801
	Version: 9 dated 07 AUG 2023
	Author: Aixial Group CRO

Physical examination	Section 8.1.3
Alcohol consumption	Section 7.7
Central Laboratory: Liver and lipid biochemistry panels Fasting conditions are required for the lipid panel.	Section 8.1.11
Local Laboratory: Liver biochemistry panel	Section 8.1.12
Vector shedding: blood, urine, saliva, feces - mandatory Note: at all visits until end of year 1, as applicable, vector shedding sampling is to occur at every site scheduled visit until 3 consecutive concerned samples are negative (at or below quantification limit).	Section 8.2.3
ELISA and IFN-gamma ELISpot	Section 8.2.4
Sirolimus	Section 7.5
Sirolimus level test: sampling for blood trough concentration 8 weeks days after starting treatment with Sirolimus	Section 7.5
Oral steroid (Prednisone or Prednisolone)	Section 7.5.1
Adverse events	Section 9.2
Concomitant medications	Section 8.1.2

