5.3 Data Derivations

Baseline and Change from Baseline

Baseline and change from baseline will be calculated for all assessments, including additional assessments (if applicable), as follows:

- Baseline value is defined as the last available value prior VTX-801 dosing, if not defined otherwise in the study protocol. Assessments that occurred on the same day as VTX-801 dosing, when time of assessment is not available, will be assumed to be prior to VTX-801 dosing (unless the assessment is planned after VTX-801 dosing in the study protocol).
- Change from baseline will be calculated for any post-baseline data as the difference between the post-baseline assessment value and the baseline value.

Study Day

Study day will be calculated as (assessment/sample date – date of first study treatment dose) for pre-baseline assessments and [(assessment/sample date – date of first study treatment dose) + 1] for post-baseline assessments, i.e., there will be no study day 0 and study day 1 will correspond to the first study treatment dose.

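### By default, the triglyceride and total cholesterol baseline is the Day -7 draw, with no visible fasting condition, while the Week 4 and Week 8 lipid draws are fasting

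*Protocol*

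**What the plan says.** Protocol 8.1.11, Table 8, lists triglycerides and total cholesterol twice: under routine blood biochemistry, with glucose and no fasting label, and under a panel headed "Lipid Panel (fasting)", with LDL and HDL. The lipid panel has a stated purpose: "In relation to the Sirolimus treatment, patients will be monitored for hyperlipidemia". The same section fixes its timing, ending "triglycerides and total cholesterol is included at Screening 1, Screening 2, Week 4 and Week 8".

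The visit lists in protocol section 10 agree. Screening 1, Screening 2 and Week 4 combine biochemistry with the lipid panel, and Week 4 carries the instruction "Fasting conditions are required for the lipid panel". Week 8 lists "Central Laboratory: Liver and lipid biochemistry panels", also fasting, but no routine biochemistry. Visit 2 (Day -7) lists "Central Laboratory: blood/urine biochemistry; hematology; coagulation", with no lipid panel and no fasting instruction in the visible text.

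SAP 5.3 states "Baseline and change from baseline will be calculated for all assessments, including additional assessments (if applicable), as follows", and then "Baseline value is defined as the last available value prior VTX-801 dosing, if not defined otherwise in the study protocol". Protocol 11.4.4.2 plans summaries of laboratory values and of their change from baseline by dose cohort.

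**The concern.** The baseline rule looks at timing only. For an analyte drawn both fasting (Screening 2) and later under no stated condition (Day -7), it passes over the fasting value. The Week 4 and Week 8 draws, the only lipid-panel draws after dosing, are then compared with a value that need not be fasting.

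Lipid rise on sirolimus is a named safety concern with its own sampling plan, and laboratory change is part of the primary endpoint (protocol 3.2.1). A change score meant to show a drug effect should not also carry a difference in fasting status.

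**Working it through.** **1. Draw conditions, from Table 8 and the section 10 visit lists**

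| Visit | Routine biochemistry | Lipid panel | Fasting stated |
|---|---|---|---|
| Screening 2 (Day -49 to Day -14) | yes | yes | yes |
| Visit 2 (Day -7) | yes | no | not in visible text |
| Visit 10 (Week 4) | yes | yes | yes |
| Visit 18 (Week 8) | no | yes | yes |
| Visit 26 (Week 12) | yes | no | not in visible text |
| Weeks 24, 36, 52 and Visits 47 to 56 | yes | no | not in visible text |

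**2. Check against the blood volumes in Table 18 (protocol 17.1.2)**

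- V2: 2 + 16 + 5 + 5 + 7 + 12 + 4 + 50 = 101 mL; the table says 101.
- V10: 16 + 5 + 5 + 3 + 7 + 12 + 4 + 1 + 4 + 50 = 107 mL; the table says 107.
- V18: 5 + 5 + 5 + 3 + 1 + 4 + 50 = 73 mL; the table says 73.

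V2 closes without a lipid row. V18 closes with the 5 mL lipid row and without the 16 mL biochemistry row, so there is no glucose at Week 8. The biochemistry row itself closes as 4 × 16 = 64 mL (V2, V8, V10, V26), so it holds no draw at V3 to V6. Day -7 is therefore the last pre-dose routine biochemistry that the documents show.

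**3. Apply the SAP 5.3 rule**

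The rule yields to a baseline defined in the protocol. The protocol defines a screening baseline for M.I.N.I. (8.1.7), abdominal MRI and elastography (8.1.8) and brain MRI (8.1.9), but not for lipids. The default applies, with two possible data structures:

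- *Results merged into one parameter per analyte.* Baseline is Day -7, so both Week 4 and Week 8 compare a fasting value with one that need not be.
- *Panels kept separate.* The lipid-panel series has a fasting Screening 2 baseline and is matched at Weeks 4 and 8. The routine-biochemistry series has a Day -7 baseline, and its Week 4 value comes from a fasting visit, so Week 4 is still mismatched.

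The documents do not say which structure applies. Volumes lean towards one shared sample: the row is 16 mL at V2 without the lipid panel and 16 mL at V10 with it, and Table 17 gives 11 + 5 = 16 mL at each screening visit with it. LDL and HDL are drawn only in the lipid panel and keep the fasting Screening 2 baseline. Glucose is not in that panel; it is touched only at Week 4, through the shared visit.

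**4. Effect on the change score**

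Let d be the Day -7 value minus what a fasting value would have been. Then

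reported change = fasting follow-up − (fasting baseline + d) = true change − d.

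The documents give no value for d. For illustration only, assume fasting triglycerides of 120 mg/dL before dosing and 180 mg/dL at Week 4, a true change of +60:

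| Assumed d (mg/dL) | Reported change for the patient | Shift in a two-patient cohort mean if one patient is affected (d/2) |
|---|---|---|
| 0 | +60 | 0 |
| 10 | +50 | −5 |
| 20 | +40 | −10 |
| 30 | +30 | −15 |
| 50 | +10 | −25 |

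A negative d would overstate the rise. If the patient fasted on Day -7, d = 0 and there is no error.

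**5. Later visits**

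Weeks 12, 24, 36 and 52 (4 visits) and Visits 47 to 56 (10 visits) have routine biochemistry with no stated fasting condition. These 4 + 10 = 14 visits are like for like with Day -7 as far as the visible text goes.

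**The case against.** The case against is substantial.

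- **Fasting on Day -7 cannot be excluded.** Protocol 10.2 refers to Table 2 and its footnotes, which are not available, and sample-collection instructions sit in the Central Laboratory Manual. No stated requirement also does not mean that a patient had eaten. This stands, and it makes the point conditional.
- **The panels may be separate parameters.** If so, the lipid-panel series already has the right baseline. This stands for Week 8. At Week 4 the routine-biochemistry series remains mismatched.
- **Laboratory tables may not show change.** SAP 7.9.2 names by-visit values and a listing; it does not name change, although SAP 7.9.4 does for ECG. By-visit values do not depend on the baseline choice. But SAP 5.3 derives change for all assessments, protocol 11.4.4.2 summarizes it, and SAP section 9 drops laboratory shift tables without dropping change.
- **Little depends on it.** Four patients were dosed, two per cohort; nothing is tested and all values are listed. Sirolimus adjustment under protocol 7.6.2 uses routine patient monitoring, not SAP change scores. This stands and limits the weight of the point.

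A reader might infer something stronger: that the plan builds in a systematic understatement of triglycerides, total cholesterol and glucose at both visits, with a false step up at Week 12. The documents do not support that. They give no direction or size for a meal effect. Understatement is plausible for triglycerides only if patients had eaten, and is not shown for total cholesterol. Glucose is not drawn at Week 8 and is not the named monitoring target. Change at Week 12 against Day -7 is like for like.

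**Conclusion.** The point holds in a limited form. For triglycerides and total cholesterol, SAP 5.3 defaults to a Day -7 baseline with no visible fasting condition, although a fasting Screening 2 value exists and the Week 4 and Week 8 lipid draws are fasting. The Week 4 mismatch holds under either data structure; the Week 8 mismatch needs the two panels to be merged.

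The resulting error is d per patient, unknown from the documents and zero for anyone who fasted on Day -7. The conclusion assumes that no Table 2 footnote or laboratory-manual instruction requires fasting at Visit 2. If one does, the concern falls away. With four patients and a descriptive analysis, this is a cheap improvement to a named safety summary, not a threat to the trial's conclusions.

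**What to change.** In SAP 5.3, add a rule for triglycerides and total cholesterol:

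- Week 4 and Week 8 change is computed against the last fasting pre-dose value: Screening 2, or Day -7 where that draw is recorded as fasting.
- Day -7 stays the baseline for Week 12 and later biochemistry visits that carry no fasting condition.
- Fasting status is flagged in the laboratory listing where it was recorded.

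State also whether biochemistry and lipid-panel results form one parameter or two. If Week 4 glucose change is shown, footnote that the Week 4 visit was fasting.

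Do not impose a single fasting baseline with a bar on all fasting-to-non-fasting change. That would remove change from baseline for these analytes at the 14 later visits in order to repair two. Advice on fasting for further patients is moot, since dosing has ended.

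Cost: a short SAP addition and a derivation flag, with no new samples. The Screening 2 baseline is nominally 14 − 7 = 7 to 49 − 7 = 42 days older than Day -7, and the tables need a footnote explaining the two baselines.

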10.4 Visit 7: Day 2, Week 1: Post-VTX-801 Administration

This is the second day of a 2-day inpatient period related to VTX-801 administration.

Refer to Table 2 Summary of Schedule of Events: Baseline to Week 12				
Visit 7	Day 2	VTX-801	Inpatient visit	Cross-reference
Vital signs				Section 8.1.4
Physical examination				Section 8.1.3
Local laboratory: Liver biochemistry panel				Section 8.1.12
Vector shedding: blood, urine, saliva, feces - mandatory Note: vector shedding sampling is to occur at every site scheduled visit until 3 consecutive concerned samples are negative (at or below quantification limit)				Section 8.2.3
Sirolimus				Section 7.5
Oral steroid (Prednisone or Prednisolone)				Section 7.5.1
Adverse events				Section 9.2
Concomitant medications				Section 8.1.2

Protocol VTX-801_CLN_001	Investigational Product: VTX-801
	Version: 9 dated 07 AUG 2023
	Author: Aixial Group CRO

10.5 Visits 8-46: Follow-up Until End of Year 1 Post-VTX-801 Administration

10.5.1 Visit 8 (Day 8 ± 2 days)

Refer to Table 2 Summary of Schedule of Events: Baseline to Week 12				
Visit 8	D8 ± 2 days	Follow-up	Outpatient visit	Cross-reference
Vital signs				Section 8.1.4
Physical examination				Section 8.1.3
Alcohol consumption				Section 7.7
Central Laboratory: Hematology				Section 8.1.11
Central Laboratory: Liver biochemistry panel				Section 8.1.11
Local laboratory: Liver biochemistry panel				Section 8.1.12
Vector shedding: blood, urine, saliva, feces - mandatory Note: at all visits until end of year 1, as applicable, vector shedding sampling is to occur at every site scheduled visit until 3 consecutive concerned samples are negative (at or below quantification limit)				Section 8.2.3
Sirolimus				Section 7.5
Sirolimus level test: sampling for blood trough concentration after 7 to 14 days according to local practice				Section 7.5
Oral steroid (Prednisone or Prednisolone)				Section 7.5.1
Adverse events				Section 9.2
Concomitant medications				Section 8.1.2

Protocol VTX-801_CLN_001	Investigational Product: VTX-801
	Version: 9 dated 07 AUG 2023
	Author: Aixial Group CRO

10.5.2 Visit 9 (Day 15 ± 2 days)

Refer to Table 2 Summary of Schedule of Events: Baseline to Week 12				
Visit 9	D15 ± 2 days	Follow-up	Home nurse visit	Cross-reference
Vital signs				Section 8.1.4
Local Laboratory: Liver biochemistry panel				Section 8.1.12
Sirolimus				Section 7.5
Oral steroid (Prednisone or Prednisolone)				Section 7.5.1
Adverse events				Section 9.2
Concomitant medications				Section 8.1.2

10.5.3 Visit 10 (Week 4 ± 2 days)

Importantly, from Week 4 to Week 12 inclusive post VTX-801 administration, liver function tests will be performed twice a week.

Additionally, in the case that an ALT increase $\geq 1.5 \times$ baseline between Week 4 and Month 6 post-VTX-801 administration occurs despite the immunosuppressive regimen (Section 7.5), site has to specifically refer to Section 7.5.2 for guidance.

Protocol VTX-801_CLN_001	Investigational Product: VTX-801
	Version: 9 dated 07 AUG 2023
	Author: Aixial Group CRO

Refer to Table 2 Summary of Schedule of Events: Baseline to Week 12				
Visit 10	Week 4 ± 2 days	Follow-up	Outpatient visit	Cross-reference
Vital signs				Section 8.1.4
Physical examination				Section 8.1.3
Alcohol consumption				Section 7.7
Central Laboratory: Blood/urine biochemistry with lipid panel; hematology; coagulation Fasting conditions are required for the lipid panel.				Section 8.1.11
Central Laboratory: Liver biochemistry panel				Section 8.1.11
Local laboratory: Liver biochemistry panel				Section 8.1.12
Ceruloplasmin (enzymatic assay and nephelometry), total Cu, REC, RAC, CuEXC, ANCC, CRP				Section 8.1.13
Anti-AAV3B capsid neutralizing antibodies				Section 8.2.1
Vector shedding: blood, urine, saliva, feces - mandatory Note: at all visits until end of year 1, as applicable, vector shedding sampling is to occur at every site scheduled visit until 3 consecutive concerned samples are negative (at or below quantification limit)				Section 8.2.3
ELISA and IFN-gamma ELISpot				Section 8.2.4
Sirolimus				Section 7.5
Sirolimus level test: sampling for blood trough concentration 28 days after starting treatment with Sirolimus				Section 7.5
Oral steroid (Prednisone or Prednisolone)				Section 7.5.1

Protocol VTX-801_CLN_001	Investigational Product: VTX-801
	Version: 9 dated 07 AUG 2023
	Author: Aixial Group CRO

Adverse events	Section 9.2
Concomitant medications	Section 8.1.2

